## Subject Recruitment and Compensation

- Describe recruitment procedures, including who will introduce the study to potential subjects. Describe how you will ensure that subject selection is equitable and all relevant demographic groups have access to study participation (per 45 CFR 46.111(a) (3)). Include information about approximately how many DUHS subjects will be recruited. If subjects are to be compensated, provide specific prorated amounts to be provided for expenses such as travel and/or lost wages, and/or for inducement to participate.

The opportunity to participate will be presented to employees by the supervisor of East Campus Dining. The opportunity will be clearly presented as voluntary and having no bearing in employment or performance evaluations. We will work with the supervisor to facilitated recruitment through assistant managers, emails, flyers, and staff meetings.

The age diversity of the sample is guided by the research question, which is oriented toward mid-to-late middle age, and aligns with the target population of the Roybal Center, which is funding entity for this pilot study. The demographics are guided by the workforce cohort chosen for the pilot study, which is based workplace demands and past participation in successful workplace activity initiatives. However, the target population is predominantly African American, which is a demographic group that is often underrepresented in intervention research on physical activity.

The target cohort for this pilot study will be composed of Duke University employees, but not DUHS employees.

#### **Participant Remuneration**

Baseline assessment (\$50), post-intervention assessment (\$70), 2-month follow-up interview (32 x \$20), non-participant interview (20 x \$20).

We plan assessment proximate to the workplace, so there will be no travel costs. The intervention occurs on paid time, and will not result in lost wages.

#### **Subject's Capacity to Give Legally Effective Consent**

- If subjects who do not have the capacity to give legally effective consent are included, describe how diminished capacity will be assessed. Will a periodic reassessment occur? If so, when? Will the subject be consented if the decisional capacity improves?

This is not applicable. All participants will have the capacity to give legally effective consent.

#### **Study Interventions**

- If not already presented in #4 above, describe study-related treatment or use of an investigational drug or biologic (with dosages), or device, or use of another form of intervention (i.e., either physical procedures or manipulation of the subject or the subject's environment) for research purposes.

The behavioral intervention is described above. There is no use of an investigational drug, biologic, or device.

#### **Risk/Benefit Assessment**

- Include a thorough description of how risks and discomforts will be minimized (per 45 CFR 46.111(a) (1 and 2)). Consider physical, psychological, legal, economic and social risks as applicable. If vulnerable populations are to be included (such as children, pregnant women, prisoners or cognitively impaired adults), what special precautions will be used to minimize risks to these subjects? Also identify what available alternatives the person has if he/she chooses not to participate in the study. Describe the possible benefits to the subject. What is the importance of the knowledge expected to result from the research?

Mobility and fitness testing has a low risk of complications, and the physical assessment in the study are widely used, including in populations with medical conditions and mobility limitations. All physical assessment are administer by a trained fitness specialist.

Brief low intensity activities will be taught during MOBA session, and have low risk of complications /injury. These are also taught by a trained fitness specialist. Participants will be choosing low-to-moderate physical activities in which they will voluntarily engage during their time out of work. Trained fitness specialists will provide guidance on a range of appropriate activities and progression of activity level. These voluntary activities will be expected to have low risk of complications/injury.

There may be risks, discomforts, or side effects that are not yet known.

Vulnerable populations will not be included in this study.

The possible benefits of participation in this study are expected to be improved mobility and decreased stationary behavior, which reduced multiple health and injury risks. The knowledge from the research is expected to result in a better understanding of how to motivate individuals to decrease stationary behavior and increase physical activity.

### Costs to the Subject

- Describe and justify any costs that the subject will incur as a result of participation; ordinarily, subjects should not be expected to pay for research without receiving direct benefit.

We do not anticipate any costs incurred by participants as a result of participation.

### Data Analysis & Statistical Considerations

- Describe endpoints and power calculations. Provide a detailed description of how study data will be analyzed, including statistical methods used, and how ineligible subjects will be handled and which subjects will be included for analysis. Include planned sample size justification. Provide estimated time to target accrual and accrual rate. Describe interim analysis including plans to stop accrual during monitoring. Phase I studies, include dose escalation schema and criteria for dose escalation with definition of MTD and DLT.

Sample size was based on previous recommendations from Lancaster et al. that targeting approximately 30 participants is a pragmatic standard for feasibility trials. While we recognize this sample size will not allow us to derive meaningful effect size estimates for between-group comparisons in this pilot study, it will be useful in determining the acceptability of the proposed intervention and deriving variance metrics (e.g., standard deviation of physical activity outcomes) for the purposes of future effect size estimation. We acknowledge that the proposed sample size is not adequate for formally testing group differences or effect size metrics. We will therefore (a) interpret these comparisons as preliminary, (b) characterize effect sizes for pre-to-post changes within each group separately, and (c) characterize group changes in actigraphy using contemporary minimum clinically important difference (MCID) metrics (e.g., 500 steps / day).

**Analysis plan for Aim 1.** We plan to collect multiple sources of information to provide information about feasibility and acceptability: (1) We will document our challenges and decisions across all aspects of the study (e.g., recruitment, engagement, obstacles to enrollment) to optimize the translation of our findings; (2) We will collect descriptive data on adherence and participant engagement; (3) We will collect and characterize descriptive information on experience, perceived benefits, and satisfaction; (4) We will conduct focus groups with participants, and those who declined to participate, to better understand "what worked" and "what needs work" with respect to the intervention. We will consult with Duke Roybal Center intervention experts for input on our approach. Areas of efficacy: We will use data from the PAST questionnaire to identify which domains of activity are most and least responsive to MOBA. Fidelity to the

treatment will be assessed by [name], who does not lead groups, but will review taped sessions to document adherence (e.g., whether content described in treatment manual is presented during sessions).

**Analysis plan for Aim 2.** To test Hypothesis 2, we will examine mean difference in SPPB and 6MWT between baseline and post-intervention performance (e.g., student's *t*-test). We will also examine percent change and effect size (e.g., Cohen's *d*). To test Hypothesis 2b, we will compare change in self-reported sedentary time between baseline and post-intervention. We will plot and visually examine trends of change across monthly questionnaires. Additionally, we will examine change in Actigraph measures between baseline and post-intervention. As part of this aim, we will examine the association between self-report (PAST) and device-measured activity.

**Analysis plan for Aim 3.** To test Hypothesis 3, we will examine mean difference, percent change, and effect size in BADS (Avoidance and Activation scales) and BBAQ total score between baseline and post-intervention assessments.

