Official Title: Movement-Oriented Behavioral Activation (MOBA) to Reduce Stationary Behavior

DUHS IRB Application Version 1.13

Pro00108020

Approval Date: 09/09/2022

NCT04892147

**Aim 1:** Determine feasibility and acceptability of a 10-week group MOBA intervention for individuals with excessive stationary behavior compared to waitlist control.

**Aim 2:** Assess activity and mobility changes following a 10-week group MOBA intervention for individuals with excessive stationary behavior compared to waitlist control.

**Hypothesis:** Individuals completing MOBA will have greater (1) improvement in physical performance, (2) reduction in sedentary time, and (3) increase in daily step count after 12 weeks compared to the control group.

**Aim 3:** Examine changes in activation, avoidance, and perceived barriers to physical activity after a 12-week group MOBA intervention for individuals with excessive stationary behavior compared to waitlist control.

**Hypothesis:** Individuals completing MOBA will have greater (1) increase in activation, (2) decrease in avoidance, and (3) decrease in self-reported barriers to physical activity after 12 weeks compared to the control group.

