#### Overview.

The study uses randomized waitlist-control design. We propose to randomly assign half of participants to (a) 10 weeks of MOBA intervention, and half of participants to (b) a 10-week waitlist, followed by 10 weeks of MOBA.

**Intervention.** MOBA is adapted from established protocols to integrate traditional behavioral activation (BA) principles with strategies to incorporate values-based, goal-directed movement into daily routines. The BA content of MOBA is adapted from co-investigator [name] intervention Behavioral Activation Therapy for Anhedonia (BATA). MOBA reduces depression-related content relative to BATA and increases focus on values that engage individuals in movement-related activity. MOBA is designed as a group intervention to leverage the reward value of social contact, and the positive influence of group problem-solving and accountability on behavior change. MOBA preserves the principles and general sequence of sessions used in BATA, but incorporates movement-oriented content: (a) provide psychoeducation about risks of physical inactivity, behavioral barriers to activity, and rationale for the treatment approach; (b) explore personal values, non-stationary, movement-oriented activities that support those values, and a hierarchical plan for goal attainment; (c) identify and assign weekly activities related to the valued goals; (d) address common barriers to engagement with valued activities including avoidance, low behavioral initiation, and an overemphasis on felt motivation as a prerequisite for action; and (e) monitor, support, and reward achieving behavioral goals. Content unique to MOBA includes: 1) demonstration and participation in physical activities that provide alternatives to stationary behavior, including select activities used in a previous study with the Dining Services cohort (e.g., stairs, body-weight squats, knee raises), and 2) generation of person-centered strategies for integrating movement-oriented activities into daily routines across the three domains of the Behavior Settings Model: 1) workplace sitting/prolonged standing, 2) screen-focused home activities, 3) time spent sitting in automobiles. Weeks 1-4 address topics a-c; weeks 5-12 address topics d-e. MOBA will be facilitated by a clinician ([name]) and a wellness educator ([name]), who will be trained on the MOBA treatment manual. The facilitators' role is to provide teaching, support, encouragement, and guidance throughout the intervention. Weekly sessions will take place in a dedicated conference room near the workplace, during the last hour of the workday (4-5 pm), and is counted as paid time at work.

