
#### Assessments.

**Pre-intervention focus group.** Separately, and prior to the enrollment in the intervention, we plan to conduct a small focus group of individuals (N = 8-10) from the Duke Dining Service staff in order to (1) better understand perspectives and experience with physical activity; (2) gauge interest in aspects of the study, and (3) understand format preferences for presenting and collecting information. The goal is to gather information to improve delivery of the intervention to participant stakeholders. Individuals who participate in the focus group are not under any obligation to participate in the intervention.

Feasibility and acceptability. We plan to collect multiple sources of information to provide information about feasibility and acceptability:

(1) We will document our challenges and decisions across all aspects of the study (e.g., recruitment, engagement, obstacles to enrollment) to optimize the translation of our findings; (2) We will collect descriptive data on adherence and participant engagement; (3) We will collect and characterize descriptive information on experience, perceived benefits, and satisfaction; (4) We will conduct focus groups with participants, and those who declined to participate, to better understand "what worked" and "what needs work" with respect to the intervention. We will consult with Duke Roybal Center intervention experts for input on our approach. Fidelity to the treatment will be assessed by [name], who does not lead groups, but will review taped sessions to document adherence (e.g., whether content described in treatment manual is presented during sessions).

Mobility testing. Short Physical Performance Battery (SPPB) will assess lower extremity function and mobility. The 6-Minute Walk Test (6MWT) will assess functional exercise capacity. These measures will occur at Baseline and Week 10.

Mechanisms of change. The Behavioral Activation in Depression Scale (BADS) will assess state characteristics of avoidance and activation. This measure will be administered at baseline and week 5. The Barriers to Being Active Quiz will assess perceived barriers to regular movement-oriented activity. These measures will be administered at baseline and post-intervention.

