Stationary behavior. With no validated questionnaire specific to stationary behavior, self-reported sedentary activity will be assessed at baseline/post-assessment, and weekly during the intervention using the Past-Day Adults' Sedentary Time questionnaire (PAST). The PAST assesses multiple domains of sedentary behavior over the past day; it was found to have the highest correlation to device-based activity compared to other questionnaires. The PAST will be administered at baseline, weekly, midpoint, and post

assessment. Device-based tracking. Participants will wear an Actigraph Actilife 6 accelerometer on the right hip for 7 days prior to MOBA participation. This period will represent the pre-intervention control activity condition for each participant. Participants will similarly wear the Actigraph for 1 week post-intervention. The main outcomes of device-based tracking will be percent change in step count per day, with secondary measures including total activity count, and physical activity energy expenditure.

MOBA intervention sessions will occur weekly.

The following questionnaires will also be administered. PHQ-9 will be collected at baseline and week 10, which is post assessment. Physical Activity Readiness will be collected at baseline. The Brief Health Questionnaire will be collected at baseline and week 10. At the final session, a MOBA Class Feedback form will be completed by the participants.

As shown in Table 1, participants will complete a baseline assessment administered by a fitness specialist that includes questionnaires and mobility testing. These assessments will be repeated at end of the intervention. Additionally, the wait-list control group will complete a third assessment at the end of their 02-week participation in MOBA.

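### The Aim 2 and 3 hypotheses compare MOBA with waitlist, but the analyses named to test them are baseline-to-post changes with no arm term and no named control endpoint

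*Combined protocol and SAP*

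**What the plan says.** The opening Aims section frames both efficacy hypotheses against the control arm. The last element of the Aim 2 hypothesis, for example, is "3) increase in daily step count after 12 weeks compared to the control group", and Aim 3 is worded the same way for activation, avoidance and barriers. The Overview under Design & Procedures supplies that control by randomising half of participants to "a 10-week waitlist, followed by 10 weeks of MOBA".

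The Aim 2 plan in Data Analysis & Statistical Considerations states: "To test Hypothesis 2, we will examine mean difference in SPPB and 6MWT between baseline and post-intervention performance", with Student's t-test as an example. Self-reported sedentary time, Actigraph measures, BADS and BBAQ are likewise examined between baseline and post-intervention. None of these sentences mentions arm, control or waitlist. Earlier in the section, the plan accepts that the sample cannot support formal group testing, says the between-group comparisons will be read as preliminary, and promises effect sizes for pre-to-post change in each group separately.

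The visits are set out under Assessments and in Table 1:

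- Mobility: "These measures will occur at Baseline and Week 10".
- BADS: "This measure will be administered at baseline and week 5". Table 1 instead lists it pre- and post-intervention.
- Actigraph: "Participants will wear an Actigraph Actilife 6 accelerometer on the right hip for 7 days prior to MOBA participation", and again for one week afterwards.
- Waitlist arm: "the wait-list control group will complete a third assessment at the end of their" own MOBA course. The note to Table 1 gives this arm three time points: start of wait, pre-intervention and post-intervention.

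**The concern.** A comparative hypothesis needs a comparative estimate. If scores rise in both arms because people have practised the SPPB and 6MWT, or because the season has changed, a baseline-to-post change in the MOBA arm includes that rise. The waitlist arm exists so that it can be subtracted, and the analyses named for Aims 2 and 3 do not subtract it.

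The visit labels add a second difficulty. In Table 1 the waitlist arm's post-intervention visit follows its own MOBA course, so on those labels its pre-to-post change is a treated change. Reporting each group separately would reveal a shared shift only if the waitlist change from baseline to pre-intervention were also shown, and the plan does not ask for it. Anyone who took the waitlist arm's final visit as its endpoint would be comparing two treated arms. No sentence plans that comparison, but none rules it out.

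**Working it through.** **1. The plan's own figure.** Selection of Subjects plans 16 people in each of two groups: 2 × 16 = 32, as stated. With 23% attrition, 16 × 0.77 = 12.3, so about 12 completers per arm; conversely 12 / 0.77 = 15.6, rounded up to 16. The documents give no alpha, SD, effect size or ICC. Everything numerical below assumes a two-sided 5% level and is shown for 12 and 16 per arm.

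**2. Hypothesis against named analysis.**

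| Outcome | Hypothesis | Named analysis |
|---|---|---|
| SPPB, 6MWT | versus control | mean difference, baseline to post |
| PAST | versus control | change, baseline to post |
| Actigraph | versus control | change, baseline to post |
| BADS, BBAQ | versus control | mean difference, percent change and effect size, baseline to post |

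**3. What each contrast estimates.** Let d be the MOBA effect, s the shift shared by both arms in the first period, and s2 any later drift.

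- MOBA arm, baseline to post: d + s.
- Waitlist arm, baseline to end of wait: s.
- Waitlist arm, baseline to its post-MOBA visit, with the same effect d: d + s + s2.

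The end-of-wait contrast is (d + s) − s = d. The contrast with the waitlist arm's final visit is (d + s) − (d + s + s2) = −s2, which is near zero without later drift, whatever d is. The MOBA-arm change alone gives d + s.

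**4. Cost of not subtracting s.** Set d = 0. The paired t-test in the MOBA arm rejects with probability P(|T| > t(0.975, n−1)), where T is noncentral t with n−1 degrees of freedom and noncentrality s√n (s in SDs of change).

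| Shared shift s | n = 12 | n = 16 |
|---|---|---|
| 0.2 | 10% | 12% |
| 0.3 | 16% | 20% |
| 0.5 | 35% | 46% |
| 0.8 | 71% | 85% |

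In the between-arm test s cancels. Simulation at s = 0.2 and 0.8 (200,000 runs) gave 5.0% throughout with independent participants.

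**5. Precision of the between-arm contrast.** The half-width of the 95% CI for a difference in change is t(0.975, 2n−2) × √(2/n):

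- n = 12: 2.074 × 0.408 = 0.85 SD of change.
- n = 16: 2.042 × 0.354 = 0.72 SD of change.

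With baseline adjustment, in SDs of the outcome, it is t(0.975, N−3) × √[(2/n)(1−r²)(1+1/(N−4))], where N = 2n. At an assumed r = 0.5 this gives 0.75 (n = 12) and 0.64 (n = 16). An unadjusted comparison at the common time point gives 0.85 and 0.72 SD of the outcome.

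**6. Clustering.** The plan states that "MOBA is designed as a group intervention", and 16 people in each of two groups suggests that the MOBA arm is a single group. A simulation (400,000 runs per cell, no effect, no shared shift, total variance 1, one group effect with variance ICC in the MOBA arm only) gave these rejection rates:

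| ICC | Between-arm, n = 12 / 16 | MOBA-only paired, n = 12 / 16 |
|---|---|---|
| 0.02 | 6.3% / 6.8% | 7.4% / 8.4% |
| 0.05 | 8.3% / 9.6% | 11.3% / 13.8% |
| 0.10 | 11.9% / 14.3% | 17.8% / 22.0% |

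With the ICC treated as known, the change-score half-width is t(0.975, 2n−2) × √[(1−ICC)/n + ICC + 1/n]. At those three ICCs it is 0.89, 0.96 and 1.05 (n = 12) or 0.77, 0.85 and 0.96 (n = 16). Clustering affects both analyses, the MOBA-only test more.

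**The case against.** The best defence is that the Aim 2 and 3 sentences are shorthand. The same section speaks of between-group comparisons to be read as preliminary, so its authors expect to make them. Student's t-test could mean a two-sample test on change scores, and the promise to compare change in sedentary time could mean comparing it between arms. Both would be valid. The within-group emphasis is also a disclosed response to a small sample, and the plan treats the week before MOBA as each participant's own control period.

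Much of this stands. The text does not exclude a between-arm analysis, and its authors do not overclaim. The shifts and ICCs used here are assumed, the plan states no significance-based conclusion, and clustering is a separate limitation that a between-arm analysis does not cure. The end-of-wait BBAQ value also rests only on the general three-visit note in Table 1 and the third-assessment sentence.

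The gap remains all the same. A preliminary comparison still needs an estimator and a control visit, and the plan gives neither. Two analysts following it faithfully could report different contrasts. A small sample is a reason for a wide interval, not for testing a comparative hypothesis without its comparator.

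**Conclusion.** The concern holds. The hypotheses are comparative, the analyses named to test them have no arm, and no sentence makes the scheduled end-of-wait visit the control endpoint. Followed literally, the plan could credit MOBA with a shift shared by both arms. The size of that error depends on a shift the documents do not give: at an assumed 0.2 SD the false-positive rate is about twice the nominal 5%, and at 0.5 SD it is 35% to 46%. The textual finding does not depend on these figures.

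The consequence is confined to Aims 2 and 3, which the plan already calls preliminary. Aim 1 is untouched. The gap should be closed before the analysis, but it does not undermine the feasibility purpose of the trial.

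**What to change.** In the Aim 2 and Aim 3 analysis plans, make the main comparative analysis the between-arm difference at the end of the randomised waiting period: the MOBA arm at its post-intervention visit against the waitlist arm at its pre-intervention visit. Analyse by assigned arm, adjust for the baseline value where one exists, give a 95% CI and label the result preliminary. Comparing change scores is also valid but usually less precise. Keep within-arm changes as description, including the waitlist change from baseline to pre-intervention, and report the waitlist post-MOBA visit separately.

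Reconcile the length of the period (10 weeks in the Overview, 12 in the hypotheses) and the Actigraph and BADS timing (Assessments against Table 1). Where no start-of-wait value was collected, compare arms at the common time point without baseline adjustment and say so. Where the waitlist arm has no waiting-period value, state that the measure has no between-arm comparison.

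**Cost.** For SPPB, 6MWT, PAST and BBAQ this changes analysis wording only, using scheduled visits; confirm that BBAQ is collected at the end of the wait. For Actigraph and BADS, first establish which waitlist values exist. The May 2022 amendment note mentions a next set of assessments, so collection may be under way and the fix should not depend on new data. Losing the Actigraph baseline would widen the half-width from 0.75 to 0.85 SD (12 per arm) or from 0.64 to 0.72 (16), at the assumed r = 0.5 with independent participants.

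**Downside.** Intervals will be wide. If the MOBA arm is one group, its group effect cannot be separated from the MOBA effect. The report should state that the CI assumes independent participants and is too narrow if outcomes cluster.

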## Selection of Subjects

- List inclusion/exclusion criteria and how subjects will be identified.

**Participants.** Inclusion: The pilot cohort will be composed of members of the Duke Dining Service staff age 30-64. The age range was chosen to target the critical window for establishing the long-term geroprotective benefits of increasing movement-oriented behaviors. The age range has also been expanded to allow for participation by all members of the Dining Service. The workplace cohort was chosen because their work demands are characterized by a high level of stationary activity, and because of previous success recruiting this group to participate in the Healthy Duke *Making the Connection* (MTC) wellness initiative. Additionally, 58% of this cohort reported >5 hours sitting per day, which indicates high levels of sedentary behavior in addition to stationary behavior at work. In MTC, the participating cohort was 72% female, and 80% were between age 30-64. Exclusion: 1) individuals with moderate or greater depression severity (PHQ-9 > 14); and 2) individuals with significant mobility limitation, defined as inability to complete 6 Minute-Walk Test. We plan to include rather than exclude individuals with medical comorbidities (e.g., diabetes, cardiac conditions, obesity) because this provides the most representative sample of the stationary population, and is consistent with our goal of developing a cross-cutting and translatable intervention. The Dining Services workforce is >90% African American, which is a group with disproportionately lower physical activity; and 3) individuals who answer "Yes" to any of the questions on the Physical Activity Readiness Questionnaire (PAR-Q) will be encouraged to consult with their physician before proceeding with the study. Physician clearance is not required for participation. Sample size. We plan to recruit 16 individuals for each of the two MOBA groups (N = 32), which allows for 23% attrition based on prior MTC completion rates.

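### The Aim 2 and Aim 3 analyses are worded as hypothesis tests on a sample the plan calls inadequate for formal testing, and no estimate or SD is given a confidence interval

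*Combined protocol and SAP*

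**What the plan says.** The opening paragraph of Data Analysis & Statistical Considerations describes a feasibility pilot. It states that "We acknowledge that the proposed sample size is not adequate for formally testing group differences or effect size metrics" and draws three consequences. Comparisons will be read as preliminary. The team will "characterize effect sizes for pre-to-post changes within each group separately". Actigraphy changes will be set against a minimum clinically important difference, with 500 steps per day as the example. The quantitative purpose it names is "deriving variance metrics (e.g., standard deviation of physical activity outcomes) for the purposes of future effect size estimation".

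The aim-level plans in the same section use different language. Aim 2 starts "To test Hypothesis 2, we will examine mean difference in SPPB and 6MWT between baseline and post-intervention performance", with Student's t-test as an example, plus percent change and Cohen's d. Hypothesis 2b is also introduced as a test, but the analysis is a comparison of change in self-reported sedentary time and a visual look at trends. Actigraph change is to be examined, with no method named. Hypothesis 3 is introduced as a test, with mean difference, percent change and effect size for BADS and BBAQ and no test named.

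The hypotheses at the front of the document, under Aims 2 and 3, are all directional and comparative: MOBA is to improve more than control. The plan states no alpha, confidence interval, multiplicity rule or criterion for support.

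**The concern.** The two parts of the section do not agree on what the analysis is for. One says the sample cannot carry formal tests of group differences; the other sets out to test hypotheses that are group differences. Reading results as preliminary is a caution, but it does not show how uncertain each number is. An interval would.

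There are two further gaps. First, the analyses are worded as baseline against post-intervention, and the stated remedy is effect sizes within each group. A within-group change does not estimate the MOBA-versus-waitlist effect that the hypotheses concern, so a clear pre-to-post gain in the MOBA arm could be taken as support without any contrast with control. Second, the SDs are the figures meant to be carried into later work, yet the aim-level plans do not list them as output, with or without an interval.

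At stake is how the pilot is read. A nominally significant change or a large d could be over-read, a non-significant one could be read as no effect, and an SD could be carried forward without its uncertainty.

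**Working it through.** **Inputs from the document.** Allocation is half and half (Overview), with 16 per group and 32 in total (Selection of Subjects). The same section allows for 23% attrition: 16 × 0.77 = 12.3, so about 12 completers per arm. The plan derives no sample size from power, so there is no calculated figure to reproduce; 2 × 16 = 32 is consistent with its target of about 30.

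**Assumptions.** Two-sided 0.05, because no alpha is stated. No outcome SD is given, so results are in units of the SD of change.

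**Between-arm difference in change.** The 95% half-width is t(0.975, 2n−2) × √(2/n).
- n = 16: 2.042 × 0.354 = 0.72 SD
- n = 12: 2.074 × 0.408 = 0.85 SD

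**Within-arm mean change.** The 95% half-width is t(0.975, n−1)/√n.
- n = 16: 2.131/4 = 0.53 SD of change
- n = 12: 2.201/3.464 = 0.64 SD of change

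**Power for a between-arm t-test at d = 0.5.** Noncentral t with 2n−2 df and noncentrality 0.5 × √(n/2).
- n = 16: noncentrality 1.414, power 28%
- n = 12: noncentrality 1.225, power 22%

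**Uncertainty of a pooled SD.** The limits are √(df/χ²) at the 0.975 and 0.025 points. With 12 per arm, df = 22:
- lower: √(22/36.78) = 0.77 times the estimate
- upper: √(22/10.98) = 1.42 times the estimate

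**Against the plan's step benchmark.** The SD of change in steps is not given. Over an assumed range of 1500 to 3000 steps per day:

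| Assumed SD | Half-width, 16 per arm | Half-width, 12 per arm |
|---|---|---|
| 1500 | ±1083 | ±1270 |
| 2000 | ±1444 | ±1693 |
| 3000 | ±2166 | ±2540 |

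Every entry exceeds twice the 500-step benchmark, so a point estimate above or below 500 says little without its interval.

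**Chance of a nominal result if nothing is happening.** With k independent tests at 0.05 the chance of at least one p < 0.05 is 1 − 0.95^k.
- SPPB and 6MWT, one arm: 1 − 0.95² = 9.8%
- Seven outcomes, one arm (SPPB, 6MWT, PAST, steps, BADS Activation, BADS Avoidance, BBAQ): 1 − 0.95⁷ = 30%

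Positive correlation between outcomes lowers both figures. The second applies only if tests are run that the plan does not name.

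**The case against.** The strongest reply is that the opening paragraph already deals with this. It disclaims formal testing and meaningful between-group effect sizes, promises a preliminary reading, and names SDs as a product. With no alpha or decision rule stated, a report that treats p < 0.05 as support would run against the plan's own commitment. That is a fair partial safeguard. It does not reconcile the test wording that follows, and it supplies no interval.

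Several stronger readings are tempting, and the documents do not support them:

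- **All the hypotheses are tested by t-test.** The t-test is an example, for SPPB and 6MWT only.
- **The plan carries a high false-positive rate.** Counting nine outcomes in both arms gives 18 tests and 1 − 0.95¹⁸ = 60%. The plan does not name those tests. The count includes activity count and energy expenditure, which the assessment section calls secondary, and waitlist-arm changes, which could not support the hypotheses.
- **Within-group effect sizes are less precise because each uses half the sample.** The working shows the reverse: 0.64 against 0.85 at 12 per arm. The objection to them is that they address a different question.
- **p-values must be banned.** Tests labelled preliminary, with intervals beside them, are a defensible choice.
- **This plan should fix how a later trial uses the SD.** That belongs to the later trial's protocol.

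**Conclusion.** The concern holds as a mismatch within one section, together with missing intervals. The test wording for Hypotheses 2, 2b and 3 conflicts with the plan's own statement about the sample. No confidence interval is planned for any change, arm difference, effect size or SD, and the between-arm contrast the hypotheses call for is not explicitly specified.

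The intervals would be informative because they are wide. Even with no dropout, a between-arm difference of half an SD could not be distinguished from zero (±0.72 SD), and a pooled SD at 12 per arm could be understated by about 40% of its value. These figures rest on two-sided 0.05, roughly normal changes, equal arms and 12 to 16 completers per arm; the step figures also rest on the assumed SD range.

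A reader might infer that the investigators intend to declare hypotheses supported on nominal significance. The documents do not say so, and the commitment to a preliminary reading points the other way. The point is worth acting on because the remedy is cheap and makes the section consistent.

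**What to change.** In the analysis plans for Aims 2 and 3:

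1. Replace the test wording for Hypotheses 2, 2b and 3 with estimation wording.
2. Report, for each outcome, the between-arm difference in change with a 95% confidence interval, and each within-arm change or effect size with a 95% confidence interval.
3. List as output the SD of each outcome and of its change, pooled over arms, with a 95% confidence interval.
4. State that any p-value shown is descriptive and will not be taken as support for or against a hypothesis.

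This needs no additional participants, visits or data. The cost is a revision of wording and slightly more output. The report could not call a hypothesis supported, but the opening paragraph of the section has already conceded that.
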